6.12 Safety Analyses

The safety analyses will be presented by the actual treatment received for the Safety Population.

6.12.1 Adverse Events

A treatment emergent adverse event (TEAE) is defined as:

- Any AE that has an onset on or after the dosing of study drug
- Any pre-existing AE that has worsened in severity on or after the dosing of study drug

A treatment-related AE is defined as an AE as being possibly related, probably related or related to the study drug. If an AE has missing relationship it is assumed to be related to the study drug for analysis purposes.

Maximum severity will be assumed for an AE with missing severity.

All AEs will be coded using Medical Dictionary of Regulated Activities (MedDRA) v22.

Summaries over system organ class (SOC) and preferred term (PT) by treatment groups, and
listings of all TEAEs, [REDACTED]

[figure not shown]
[REDACTED] SAEs, AEs leading to
death, and AEs leading to study discontinuation will be presented. The following tables will be
presented for AEs:

- Overall incidence and the number of TEAEs, treatment-related TEAEs, SAEs, Treatment-related SAEs, [REDACTED] TEAEs leading to study discontinuation, and TEAEs leading to death
- TEAE by system organ class and preferred term, incidence and number of events
- Treatment related TEAE by system organ class and preferred term, incidence and number of events
- Serious TEAE by system organ class and preferred term, incidence and number of events
- Treatment-related Serious TEAE by system organ class and preferred term, incidence and

- [REDACTED]
- Treatment-related TEAE by system organ class, preferred term and maximum severity,

- TEAEs leading to study discontinuation by system organ class and preferred term, incidence
- Listing of Serious AEs (presented in the Table section of the appendices)
- Listing of AEs leading to study discontinuation (presented in the Table section of the appendices)
- Listing of AEs leading to Deaths (presented in the Table section of the appendices)

In counting the number of AEs reported, a continuous event (i.e. reported more than once and which did not cease), will be counted only once; non-continuous AE reported several times by the same subject will be counted as multiple events.

[figure not shown]
All AEs will be listed.

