12.3.1.2 ADVERSE EVENTS AND SERIOUS ADVERSE EVENTS

12.3.1.2.1 DEFINITION OF ADVERSE EVENTS (AE)

For this protocol, an AE is any untoward medical occurrence (e.g., sign, symptom, disease, syndrome, intercurrent illness, clinically significant abnormal laboratory finding, injury or accident) that emerges or worsens following administration of IP and until the end of study participation that may not necessarily have a causal relationship to the administration of the IP. An AE can therefore be any unfavorable and/or unintended sign (including a clinically significant abnormal laboratory result), symptom, or disease temporally associated with the use of an IP, whether or not considered related to the IP. A treatment-emergent AE is one that occurs after any period of exposure to treatment.

Pre-existing conditions, which increase in frequency or severity or a change in nature as a consequence of an IP use will also be considered an AE.

An unexpected AE is an adverse reaction, the nature or severity of which is not consistent with the applicable product information (e.g., Investigator's Brochure for an unapproved IP or package insert/summary of product characteristics for an approved product).

Any clinically significant change in the study safety evaluations, (e.g., vital signs, laboratory results, ECG, injection site evaluation, physical/neurological examinations, etc.) post-treatment must be reported as an AE.

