12.3.1.2.4 TIME PERIOD AND FREQUENCY FOR EVENT ASSESSMENT AND FOLLOW-UP

The occurrence of an AE or SAE may come to the attention of investigator site staff during study visits and interviews of a subject presenting for medical care, or upon review by the blinded monitor.

All AEs including local and systemic reactions not meeting the criteria for SAEs will be captured on the appropriate CRF. Information to be collected includes event description, time of onset, clinician's assessment of severity, relationship to study product (assessed only by those with the training and authority to make a diagnosis), and time of resolution/stabilization of the event. All AEs occurring while on study must be documented appropriately regardless of relationship. All AEs will be followed to adequate resolution.

Any medical condition that is present at the time that the subject is screened will be considered as medical history and not reported as an AE. However, if the subject's condition deteriorates at any time following injection at their Day 1 Treatment visit will be recorded as an AE.

Changes in the severity of an AE will be documented to allow an assessment of the duration of the event at each level of severity to be performed. AEs characterized as intermittent require documentation of onset and duration of each episode.

The PI or investigator site staff will record all reportable events with start dates occurring any time after informed consent is obtained until 7 (for non-serious AEs) or 30 days (for SAEs) after the last day of study participation. At each study visit, the PI or investigator site staff will inquire about the occurrence

of AE/SAEs since the last visit. Events will be followed for outcome information until resolution or stabilization.

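### For an AE that begins before dosing and continues through it, the SAP's missing-severity rule and severity-only test can keep post-injection worsening out of the TEAE tables

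*SAP*

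**What the plan says.** SAP 6.12.1 gives two routes to treatment-emergent status. The first is by date: "Any AE that has an onset on or after the dosing of study drug". The second is by worsening: "Any pre-existing AE that has worsened in severity on or after the dosing of study drug". The same section adds: "Maximum severity will be assumed for an AE with missing severity". No exception for pre-dose severity is visible, although part of the section is blacked out. On counting, it says that "a continuous event (i.e. reported more than once and which did not cease), will be counted only once", while repeated non-continuous reports count as separate events.

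The protocol is worded differently. Section 12.3.1.2.1 says of emergence: "A treatment-emergent AE is one that occurs after any period of exposure to treatment". It also counts as AEs "Pre-existing conditions, which increase in frequency or severity or a change in nature as a consequence of an IP use". Section 12.3.1.2.4 says that the site "will record all reportable events with start dates occurring any time after informed consent is obtained". It sets apart what the subject already had at screening, which goes down as history rather than as an AE. If such a condition gets worse after the Day 1 injection, that is recorded as an AE. Each episode of an intermittent AE has its own onset, and changes in an AE's severity must be documented. Section 12.3.1.2.3 grades severity as mild, moderate or severe.

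SAP 3.4 makes the frequency, severity and relatedness of TEAEs, over the first 8 weeks and over the whole study, a safety endpoint.

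**The concern.** Assuming the worst severity when the grade is missing is normally a safeguard: it stops an ungraded event from looking trivial. In a before-and-after comparison the effect depends on which side is missing. If the pre-dose grade is missing, setting it to the top of the scale leaves no room for the event to worsen, so the safeguard works against its purpose.

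The second criterion is also narrower than the protocol's description of a worsened condition. A continuing pre-dose AE that changes in character after injection, at the same grade, meets the protocol's description if the change is attributed to the product, yet fails the SAP's test.

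At stake is whether such events appear in the TEAE tables, including the related and serious TEAE tables that are subsets of them. Those tables report the stated safety endpoint.

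**Working it through.** The plan gives no figure on this point, so there is nothing to reproduce. The check has three parts.

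**1. Which AEs depend on the second criterion?** Inputs are Protocol 8.5 (up to 14 days of screening, 7 days of run-in with 3 more allowed), Protocol 12.3.1.2.4 and SAP 6.12.1.

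- Condition present at screening: medical history. Its deterioration after injection is recorded as an AE. If dated from the deterioration, it meets the first criterion whatever its grade.
- Intermittent AE: each episode has its own onset, so a post-dose episode meets the first criterion.
- AE starting after consent and before dosing, and carried through injection as one continuing record: its onset is pre-dose, so only the second criterion can make it treatment-emergent.

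Only the third group is exposed. With the full screening period, the window in which such an AE can start is 14 + 7 = 21 days to 14 + 10 = 24 days.

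**2. What does the missing-severity rule do to that group?** Score mild = 1, moderate = 2, severe = 3, and missing = 3 under the SAP rule. The second criterion is met when the post-dose score exceeds the pre-dose score.

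| Pre-dose grade | Post mild | Post moderate | Post severe | Post missing (3) | Qualifying |
|---|---|---|---|---|---|
| Mild (1) | no | yes | yes | yes | 3 of 4 |
| Moderate (2) | no | no | yes | yes | 2 of 4 |
| Severe (3) | no | no | no | no | 0 of 4 |
| Missing, set to 3 | no | no | no | no | 0 of 4 |
| Missing, set to 1 instead | no | yes | yes | yes | 3 of 4 |

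The row for a known severe AE is simply the top of a three-level scale. The row for a missing pre-dose grade results from the rule. The column for a missing post-dose grade shows the rule acting conservatively: a mild or moderate pre-dose AE then counts as worsened.

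**3. What does the severity-only test leave out?** The protocol names three kinds of change in a pre-existing condition.

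- Severity: tested by the SAP.
- Frequency: an event that recurs has separately dated episodes, so post-dose ones enter by the first criterion. An event that never stopped has no episodes to become more frequent. Little is left here.
- Nature: not tested. A continuing AE that changes character at an unchanged grade is missed, unless the site opens a new record with a post-dose onset.

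**The case against.** The strongest reply is that the gap is nearly empty. Protocol 12.3.1.2.1 defines an AE as something that emerges or worsens after the product is given, and Protocol 12.3.6 sends examination findings from before dosing to the medical history page. On that footing, deterioration is a new post-dose AE and the first criterion catches it. Severity is collected for each AE, and missing data are queried (Protocol 14.1.7.1.1), so a missing pre-dose grade should be rare. The missing-severity rule speaks of an AE, not of one side of a comparison. The protocol's wider wording says when a condition becomes an AE, not when an AE is treatment-emergent, and covers only change caused by the product. Part of SAP 6.12.1 is blacked out and SAP 6.2.4 to 6.2.6 cannot be seen, so a dating or imputation rule may exist there.

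Most of this stands, and it limits the point. It does not remove it. Recording starts at consent, and the SAP's own second criterion presupposes AEs that began before dosing. Since changes in severity are documented, one AE can carry more than one grade, and the visible rule makes no pre-dose exception.

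Three stronger readings are tempting, and the documents do not support them:

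- A reader might infer that post-dose worsening in general drops out of the TEAE endpoint. It does not: worsened screening conditions and separately logged episodes can enter by date of onset.
- A reader might infer that both rules always understate TEAEs. The table above shows the missing-severity rule acting the other way when the post-dose grade is missing.
- A reader might take the counting rule as fixing a pre-dose onset for a continuous event. It governs how events are counted and assigns no onset date or TEAE status. Whether a worsened AE keeps its original date depends on CRF practice, which is not visible.

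**Conclusion.** The point holds in a narrow form and is minor. For an AE that starts between consent and dosing and continues as one record, a missing pre-dose grade blocks the worsening route completely (0 of 4 post-dose states), and a change in nature at the same grade is not tested.

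This rests on four assumptions: the record keeps its pre-dose onset date; the missing-severity rule is applied as written to the pre-dose grade; the site does not open a new record at the change; and nothing in the blacked-out text says otherwise.

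The number of events cannot be computed. The documents give no AE rate, no share of AEs ongoing at injection and no rate of missing grades, so any percentage would only reflect the values assumed for these. It is probably very small. Nothing disappears from the report: all AEs are listed, serious AEs have their own listing, and the overall table counts SAEs without requiring them to be treatment-emergent. A listing is still not the endpoint table, so the rule is worth correcting. The primary efficacy analysis is unaffected.

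**What to change.** Make two changes in SAP 6.12.1.

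1. Apply the maximum-severity assumption only to severity on or after dosing. For the worsening test, take a missing pre-dose severity as mild.
2. Extend the second criterion to cover worsening in severity or frequency, or a change in nature, in line with Protocol 12.3.1.2.1. State that the date of worsening is the TEAE onset date, which also places the event correctly in the 8-week or overall summary.

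The cost is two sentences and a small programming change. TEAE counts may rise slightly in any arm. The first change has a small downside: an AE that was moderate or severe throughout, but lacks a pre-dose grade, would count as treatment-emergent although it did not change. That errs in the conservative direction, which is what the missing-severity rule appears to intend. If a blacked-out part of the SAP already covers either matter, a cross-reference is enough.

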8.7 END OF STUDY DEFINITION

Study completion may occur at Week 8 (“early study completers” who have no treatment benefit based on NPRS) or at Week 24 (“study completers”):

Week 8 Early Study Completers:

- No Treatment Benefit:
 - Subjects who do not demonstrate improvement at Week 8, where improvement is defined as any decrease from baseline on NPRS score
 - A subject may also complete the study at Week 8 based on the investigator’s clinical judgment of no clinical improvement following treatment, regardless of whether the subject showed a treatment benefit based on the NPRS score evaluation described above.

Week 24 Study Completers:

- Treatment Benefit: Subjects who demonstrate improvement at Week 8, defined as any decrease from baseline on NPRS score, should continue in the study for follow-up until Week 24 and will be considered “complete” following the conclusion of their Week 24 visit.

For subjects who choose to discontinue from the study prior to these timepoints for any reason, every effort should be made to complete the Week 24/ET visit.

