3.4 Safety Endpoints

- Frequency, severity and relationship to study drug of treatment-emergent adverse events during the first 8 weeks post treatment and the overall study duration
- Frequency, severity and relationship to study drug of treatment-emergent serious adverse events during the first 8 weeks post treatment and the overall study duration

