6.1.5 Completed Subject

Study completion may occur at Week 8 or at Week 24. Thus, there will be two types of completers in the study, and they are as follows:

- Week 8 Early Study Completers: subjects who do not demonstrate improvement at Week 8, either based on the NPRS score (i.e. no change or worsening of the NPRS score from baseline) or on the investigator's clinical judgment of no clinical improvement following treatment, regardless of whether the subject showed a treatment benefit based on the NPRS score evaluation. These subjects complete the study at Week 8. Assessments for Week 8 visit are recorded under the Week 24/ET visit for these subjects. However, for the analysis, this will be remapped back to Week 8 visit.
- Week 24 Study Completers: subjects who demonstrate improvement at Week 8, defined as any decrease from baseline on NPRS score, and continued in the study for follow-up until conclusion of Week 24 visit.

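### The overall-study AE tables visible in the SAP give crude incidence by arm although planned follow-up is 8 or 24 weeks depending on Week 8 response, so the arm with more improvers may show a false AE excess

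*SAP*

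**What the plan says.** SAP 3.4 sets two safety windows: "Frequency, severity and relationship to study drug of treatment-emergent adverse events during the first 8 weeks post treatment and the overall study duration". A parallel endpoint covers serious events.

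Follow-up length depends on response. Protocol 8.7 ends the study at Week 8 for "Subjects who do not demonstrate improvement at Week 8, where improvement is defined as any decrease from baseline on NPRS score". SAP 6.1.5 describes the pain-score criterion as "no change or worsening of the NPRS score from baseline" and states: "These subjects complete the study at Week 8". Both documents also let the investigator end participation at Week 8 on a clinical judgment of non-response, whatever the pain score shows. Improvers are followed to Week 24.

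AE recording follows study exit. Protocol 12.3.1.2.4 keeps it open "until 7 (for non-serious AEs) or 30 days (for SAEs) after the last day of study participation".

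In SAP 6.12.1 a TEAE is "Any AE that has an onset on or after the dosing of study drug", with no end of window in the visible definition. A main table is "TEAE by system organ class and preferred term, incidence and number of events". The visible list contains no person-time denominator, no time-to-event method for AEs and no table limited to the first 8 weeks. SAP 6.9 (exposure) covers injection details only and does not summarise follow-up time. SAP 6.4 does count Week 8 and Week 24 completers by arm.

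**The concern.** Time at risk over the whole study is set by an outcome observed after randomization, and that outcome should differ by arm if the drug works. A subject who improves has about three times the planned follow-up of one who does not, and so more opportunity to report an AE. Subjects with an AE and total events may therefore both rise in the arm with more improvers even when the true AE risk is the same. With two doses under study, a difference in efficacy between doses could likewise resemble a dose-related AE pattern. The trial objective includes comparing safety with placebo, so these tables will be read across arms even though they are descriptive.

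**Working it through.** The documents give no AE rate, no Week 8 exit share and no AE timing, so there is no figure of the plan's own to reproduce. The check asks how large a difference the crude tables would show when the true AE hazard is the same in both arms.

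**Inputs from the documents:** planned follow-up of 8 or 24 weeks (Protocol 8.7, SAP 6.1.5).

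**Assumptions:** share *s* exiting at Week 8 is 15% on drug and 30% or 40% on placebo; 30% of subjects followed to Week 24 have a first AE by then; hazard *h* up to Week 8 and *k·h* afterwards, with *k* = 1, 0.25 or 0.10.

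**Formulas**
- Mean follow-up = 8s + 24(1 − s)
- h = −ln(0.7) / (8 + 16k)
- I8 = 1 − exp(−8h), and I24 = 0.30
- Crude overall incidence = s·I8 + (1 − s)·I24
- False excess = (s on placebo − s on drug) × (I24 − I8)

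**Mean follow-up:** 21.6 weeks at s = 15%, 19.2 at 30%, 17.6 at 40%. The drug arm has 21.6/19.2 = 1.13 to 21.6/17.6 = 1.23 times the follow-up of placebo.

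| Late hazard k | I8 | Drug (15% exit) | Placebo (30% exit) | Placebo (40% exit) | False excess, points |
|---|---|---|---|---|---|
| 1 | 11.2% | 27.2% | 24.4% | 22.5% | 2.8 to 4.7 |
| 0.25 | 21.2% | 28.7% | 27.3% | 26.5% | 1.3 to 2.2 |
| 0.10 | 25.7% | 29.4% | 28.7% | 28.3% | 0.6 to 1.1 |

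Excesses are computed before rounding. For k = 1, for example, 0.15 × (0.300 − 0.112) = 0.028 and 0.25 × 0.188 = 0.047. The formula gives zero when the exit shares are equal, or when no AE starts after Week 8 (I24 = I8).

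**Capture tail.** Adding the 7 days for non-serious AEs makes the windows 9 and 25 weeks. At k = 1 incidence is then 28.3% on drug against 25.5% and 23.6%, an excess of 2.8 to 4.6 points, so the tail changes little.

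**Sensitivity to the AE level and exit gap.** With constant hazard, 8-week incidence of 10% to 40%, and exit shares from 20% versus 10% to 50% versus 10% (placebo versus drug), the excess runs from 1.7 to 15.4 points. The table above is therefore not an upper bound.

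**The 8-week window.** Planned follow-up to Week 8 is the same for everyone, so in all these scenarios both arms show I8 and the difference is zero.

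**Would one pooled person-time rate repair the overall period?** Treating h and k·h as event rates, the all-event rate is [8h + (1 − s)·16·k·h] / [8s + 24(1 − s)]. At k = 1 it is 1.49 per 100 person-weeks in every arm. At k = 0.25, h = 0.0297 per week, and:
- drug: 0.339/21.6 = 1.57 per 100 person-weeks
- placebo, 30% exit: 0.321/19.2 = 1.67
- placebo, 40% exit: 0.309/17.6 = 1.76

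With no true difference, the drug arm now looks safer, because its extra person-time falls in the low-hazard period. Rates split at Week 8 do not have this fault: in this model they are h and k·h in every arm.

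**The case against.** Four points can be made for the plan, and each stands in part.

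- **An equal-window comparison already exists.** The first-8-weeks window is a named endpoint for both TEAEs and serious TEAEs. A reader might infer that the plan has no fair AE comparison; SAP 3.4 shows otherwise. What remains open is that the visible part of 6.12.1 has no 8-week table and does not say which window carries the comparison.
- **Redaction.** Some lines and table entries in 6.12.1 are blacked out or cut short, so an 8-week or exposure-adjusted table may be there. A reader might infer that the SAP omits any adjustment; that cannot be established. The unredacted tables are nevertheless crude.
- **The tables are descriptive.** No AE test is visible, completers are counted by arm, all AEs are listed and study day is derived from dosing. The imbalance is therefore not hidden and onset times can be recovered. This is a risk of misreading, not of type I error.
- **AEs after a single injection may occur early.** The documents give no AE timing, but an early concentration is plausible and would shrink the bias, as the smaller values of k show. It removes the bias only if no AE starts after Week 8.

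**Conclusion.** The concern holds in a conditional form. Read as written, the crude overall-study tables are not directly comparable between arms when exit shares differ and some AEs start after Week 8. Under the stated assumptions the false excess is about 0.6 to 4.7 points. The exit shares, the 30% incidence and the late hazard are all assumptions, and other values give smaller or larger figures.

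A reader might infer that a more effective arm will necessarily look less safe. The documents do not support that: they give neither exit shares nor AE timing, and the bias is zero in the two cases named above. The first-8-weeks endpoint is not subject to the problem, and the primary efficacy result is untouched. The change is still worthwhile, because one of the two stated safety windows is affected and the remedy is cheap.

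**What to change.** In SAP 6.12.1:

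1. Name first-8-weeks tables for TEAEs and serious TEAEs as the main between-arm comparison. If a redacted line already does this, confirm it.
2. For the overall period, add follow-up time by arm. Add also either Kaplan-Meier estimates of time to first event, censored at the end of AE capture, or person-time rates reported separately for weeks 0 to 8 and after Week 8. Do not rely on one pooled person-time rate.
3. State that figures after Week 8 describe only the subjects who stayed in the study, a group selected by response.
4. Footnote the crude overall tables to say that incidence is not directly comparable between arms because follow-up depends on Week 8 response.

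The cost is SAP wording and a few extra tables from data already collected.
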